8.2.4.1 Estimand’s attributes

Estimated on the RS. The same considerations mentioned in Section 8.2.3, except the endpoint which in this case is considered: Response defined as platelet count $\geq 30 \times 10^9/L$ and at least a 2-fold increase of the Baseline count confirmed on at least 2 separate occasions at two adjacent nominal visits at least 7 days apart, and absence of bleeding. Endpoint will be descriptively summarized.

8.2.4.2 Sensitivity analysis

Sensitivity analysis will no longer be performed.

8.2.5 Time to first rescue therapy

Definitions:

Time to first rescue therapy (in days) is defined as: Date of first rescue therapy use - Date of first treatment + 1.

Participants who are withdrawn due to TEAEs will be censored at the start date of the TEAE, and participants who do not take rescue therapy will be censored at the date of withdrawal/study completion. Where there are several AEs which led to drop out, consider the earliest starting AE.

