6.4.3 Rescue therapy

Rescue treatment will be given as per standard of care and at the discretion of the investigator as described below. If such rescue therapy is given, the participant is allowed to continue IMP treatment (as per guidance below), and should continue to complete all remaining scheduled visits in the Treatment Period, as per the Schedule of Activities (Section 1.3). The following rescue therapies may be used:

- Any increase in concomitant ITP therapies above Baseline dose
- Any additional ITP medication/therapies including but not limited to:
 - Platelet transfusion (only in cases of severe bleeding)
 - Commercially available IVIg
 - Any systemically administered corticosteroids (above the background doses, ie, pulse, oral and iv steroids). Any systemic corticosteroids used for the management of infusion reactions or other medical conditions are also considered rescue therapy.
 - Immunosuppressants (except for those listed in Section 6.4.2).

Although the use of rescue therapy is allowable at any time during the study, the use of rescue therapy should be delayed, if possible, for at least 2 days following the administration of study treatment.

If IVIg, high dose corticosteroids, or platelet transfusion are given as rescue therapy, IMP treatment can commence at the same dose as previously when platelet counts are $<50 \times 10^9/L$. Dose can be up-titrated at a later timepoint, if needed, depending on platelet level.

A high dose of corticosteroids is defined as any iv administration of corticosteroids given for any reason or doubling of an oral dose resulting in a dose more than 20mg/day prednisone equivalent dose.

In case of an increase of Baseline oral corticosteroids, not resulting in doubling of the oral dose more than 20mg/day prednisone equivalent dose, an increase in the concomitant ITP therapies above Baseline, or in case of administration of immunosuppressants as rescue therapy, IMP administration can continue as per Schedule of Activities (Section 1.3) at a dose adjusted depending on the platelet level.

The date and time of rescue therapy administration as well as the name and dosage regimen of the rescue therapy must be recorded in the eCRF.

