Platelet Count	Sensitivity	Response defined as platelet count ≥30×10 ⁹ /L and at least a 2-fold increase of the Baseline count confirmed on at least 2 separate occasions at two adjacent nominal visits at least 7 days apart, and absence of bleeding.	RS who were randomized to rozanolixizumab weekly dosing compared against those who received placebo	A composite strategy as described for Clinically Meaningful Response by Day 8 will be used.	Difference in the proportion of participants between treatment arms who have achieved a durable platelet count analyzed using logistic regression model adjusting for the covariates treatment, splenectomy, and degree of thrombocytopenia (platelet count < or ≥15×10 ⁹ /L).

Objective Clinical Category	Statistical Category	Estimand			
		Variable/Endpoint	Population	IES ^a	PLS ^b (Analysis)
Rescue therapy	Secondary	Time to first rescue therapy.	RS who were randomized to rozanolixizumab weekly dosing compared against those who received placebo.	A composite strategy will be used where, in the case rescue therapy are taken, only the platelet data up to the start date of rescue therapy will be utilized for the statistical analysis. Participants who take rescue therapy or who are withdrawn due to TEAEs are defined as having a loss of clinically meaningful platelet response and will be censored at the time of the event.	Time to first rescue therapy use will be analyzed using a stratified Log Rank Test model with fixed terms for treatment, splenectomy, degree of thrombocytopenia (platelet count < or ≥ 15×10 ⁹ /L). Estimated hazard ratios and 95% CIs will be presented. The time to first rescue therapy use will be presented graphically using a Kaplan-Meier curve.

Objective Clinical Category	Statistical Category	Estimand			
		Variable/Endpoint	Population	IES ^a	PLS ^b (Analysis)

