3.9 Changes to protocol-defined analyses

(1) Analysis sets

- (1.2) The FAS was removed from analysis
- (1.3) The PD-PPS was removed from analysis

(2) Added COVID-19 as an intercurrent event to all endpoints

(3) Note: The study was terminated early after 33 participants were randomized to bi-weekly infusions per Protocol Amendment 2; no participants were randomized to weekly infusions in the study per Protocol Amendment 3.

(4) No formal statistical analyses of efficacy endpoints were conducted. Only the primary and secondary efficacy endpoints were summarized descriptively and listed. Protocol-defined analyses for efficacy endpoints are described below.

The primary efficacy analysis of the study was planned to conduct a Stratified Cochran-Mantel-Haenszel test statistic. Sensitivity, supplemental and subgroup analyzes were planned to test the robustness of the assumption. The secondary efficacy analyses were planned to conduct a sequential hierarchical test procedure to protect the overall significance level for the multiplicity of endpoints.

Primary and secondary efficacy endpoints listed below will be listed and summarized descriptively for study participants randomized to bi-weekly dosing according to previous protocol versions.

- Durable Clinically Meaningful Platelet Response of $\geq 50 \times 10^9/L$ for at least 8 out of 12 weeks during the last 12 weeks (Week 13 to 25)
- Cumulative number of weeks with Clinically Meaningful Platelet Response of $\geq 50 \times 10^9/L$ over the 24-week treatment period (Week 1 to Week 25)
- Time to first Clinically Meaningful Platelet Response of $\geq 50 \times 10^9/L$: time from starting treatment to achievement of first response of $\geq 50 \times 10^9/L$
- Clinically Meaningful Platelet Response of $\geq 50 \times 10^9/L$ by Day 8

-
- Response defined as platelet count $\geq 30 \times 10^9/L$ and at least a 2-fold increase of the Baseline count confirmed on at least 2 separate occasions at two adjacent nominal visits at least 7 days apart, and absence of bleeding by visit
 - Time to first rescue therapy
 - Change from Baseline to Week 25 in ITP Patient Assessment Questionnaire (ITP-PAQ) Symptoms Score

Other efficacy endpoints listed below will be listed and summarized descriptively as well.

- Cumulative number of weeks over the planned 24-Week treatment period with platelet counts $\geq 30 \times 10^9/L$ and at least doubling from Baseline
- Mean change from Baseline in platelet count by visit

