8.2.5.1 Estimand’s attributes

The same considerations for treatment conditions and population of interest as mentioned in items 1 and 2 in Section 8.1.1, except the endpoint which is described above and the following approach for ICE (see Table 8-5) and the population level summary:

Table 8-5: Intercurrent Events (ICE), Intercurrent Events Strategies (ICES) and Missing data Strategies for the analysis of Time to first rescue therapy

Intercurrent Events (ICE)	ICE Strategy	Missing data strategy
a) Withdrawal from the study due to TEAE	A composite strategy: Participants will be considered censored at the time of the ICE.	Not applicable
b) COVID-19*	A composite strategy:	Section 4.2.2

* COVID-19 Impact category: Temporary discontinuation of study drug, Permanent discontinuation of study drug, Termination of study participation and Relationship to COVID-19: confirmed, suspected, general or other as recorded in the COVID-19 impact eCRF form.

Population level summary: Endpoint will be descriptively summarized. Median time to event will be estimated using the Kaplan-Meier estimate.

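### SAP 8.2.5 censors TEAE withdrawals at TEAE onset while Table 8-5 censors at the withdrawal; the onset rule discards rescue given in between

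*SAP*

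**What the plan says.** SAP 8.2.5 defines the time as the date of first rescue minus the date of first treatment plus 1. For participants who leave because of adverse events it says: "Participants who are withdrawn due to TEAEs will be censored at the start date of the TEAE". The same sentence goes on: "participants who do not take rescue therapy will be censored at the date of withdrawal/study completion". A tie-break follows: "Where there are several AEs which led to drop out, consider the earliest starting AE".

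Table 8-5 in SAP 8.2.5.1 lists the intercurrent event as "Withdrawal from the study due to TEAE", with the strategy "Participants will be considered censored at the time of the ICE". It gives no calendar date.

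Protocol Table 9-2, for the same endpoint, says that participants "withdrawn due to TEAEs are defined as having a loss of clinically meaningful platelet response and will be censored at the time of the event". It does not mention TEAE onset. (The same protocol sentence also covers participants who take rescue. They are the events of this endpoint, so that part cannot apply here.)

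SAP 3.9 lists the changes to protocol-defined analyses and includes none to this rule. It also sets the status of the result: "Only the primary and secondary efficacy endpoints were summarized descriptively and listed". SAP 8.2.5.1 asks for a descriptive summary and a Kaplan-Meier median.

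**The concern.** TEAE onset and study withdrawal are usually different days, so two programmers working from adjacent paragraphs can produce different censoring dates.

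The larger problem is the onset rule itself. The restriction to participants without rescue sits only in the second clause of the 8.2.5 sentence. The TEAE clause has no such restriction. A participant with TEAE onset, then rescue, then withdrawal is therefore censored at onset and the rescue is lost. That participant was still being followed when rescue was given, and the censoring date is chosen using something that happened later, the withdrawal. Because one TEAE can prompt both rescue and withdrawal, the censoring can be informative.

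The sequence is plausible:

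- Protocol 6.4.3 allows platelet transfusion for severe bleeding and counts systemic corticosteroids given for infusion reactions or other conditions as rescue. Protocol 7.1.3 requires permanent discontinuation for life-threatening bleeding and for severe reactions.
- Protocol 6.4.3 lets participants continue study treatment after rescue. Some stopping routes take time: Table 10-3 includes a raised ALT that persists for at least 4 weeks, and Protocol 7.1.3 includes recurrent severe headache. If repeated episodes are recorded as separate AEs leading to drop-out, the earliest-AE sentence moves censoring back to the first.

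One limit applies. Under SAP 6.6.2 a treatment counts as rescue only if it is ticked as rescue on the CRF.

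**Working it through.** The documents give no figure for this rule, so there is nothing to reproduce. The check compares the rules and then illustrates their effect on assumed data.

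**1. The rules side by side**

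| Source | Event named | Censoring date |
|---|---|---|
| SAP 8.2.5, first clause | withdrawal due to TEAE | TEAE start (earliest if several) |
| SAP 8.2.5, second clause | no rescue taken | withdrawal or completion |
| SAP Table 8-5, row a | study withdrawal due to TEAE | time of that event |
| Protocol Table 9-2 | withdrawal due to TEAEs | time of the event; onset not mentioned |

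A TEAE withdrawal without rescue meets both clauses of the 8.2.5 sentence, which give two dates. SAP Table 8-3, for the other time-to-event endpoint, has the same withdrawal row and uses data up to the start of the intercurrent event, not of the AE.

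**2. One participant (assumed dates).** TEAE onset Day 60, first rescue Day 62, withdrawal Day 65. Under 8.2.5 the record is censored on Day 60. Under Table 8-5 it is an event on Day 62.

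**3. One rescue lost.** Assume arms of 22 and 11 (33 split 2:1; the actual split is not given), *d* rescues among *n*, and no other censoring before the last rescue. With all rescues kept, cumulative rescue is *d*/*n*. If the rescue in position *k* becomes a censoring just before it would have occurred, the product-limit survival after the last rescue is

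S = [(n − k + 1)/n] × [(n − d)/(n − k)].

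| n | d | All kept | Lost at k = 1 | Lost at k = d |
|---|---|---|---|---|
| 11 | 4 | 4/11 = 36.4% | 1 − 7/10 = 30.0% | 1 − 8/11 = 27.3% |
| 11 | 6 | 6/11 = 54.5% | 1 − 5/10 = 50.0% | 1 − 6/11 = 45.5% |
| 22 | 9 | 9/22 = 40.9% | 1 − 13/21 = 38.1% | 1 − 14/22 = 36.4% |
| 22 | 11 | 11/22 = 50.0% | 1 − 11/21 = 47.6% | 1 − 12/22 = 45.5% |

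Take the median as reached when S ≤ 0.5. For n = 11, d = 6, positions 1 to 6 give 50.0, 49.5, 48.9, 48.1, 47.0 and 45.5%, so the median is lost in 5 of 6 positions. For n = 22, d = 11 it is lost in all 11. At any other *d* it does not go from reached to not reached. Its date can still move: with 7 rescues in 11, losing the sixth moves the median from the sixth rescue (S = 5/11 = 0.455) to the seventh (S = 6/11 × 4/5 = 0.436).

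**4. Several rescues lost.** Arm of 11 with three other rescues (Days 20, 70, 120) and three TEAE withdrawals (onset Days 40, 50, 60, rescue 3 days after onset, withdrawal 10 days after onset). Onset rule: S = 10/11 × 6/7 × 5/6 = 0.649, cumulative rescue 35.1%, median not reached. Withdrawal rule: 6/11 = 54.5%, median Day 120.

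**5. TEAE withdrawal without rescue.** One such participant, with one other participant's rescue between onset and withdrawal.

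- n = 11, d = 4, around the first rescue. Onset: S = 9/10 × 8/9 × 7/8 × 6/7 = 0.600 (40.0%). Withdrawal: S = 10/11 × 8/9 × 7/8 × 6/7 = 0.606 (39.4%). Difference 0.6 points.
- n = 11, d = 4, around the fourth rescue. Onset: S = 8/11 × 6/7 (37.66%). Withdrawal: S = 7/11 (36.36%). Difference 1.3 points.
- n = 22, d = 9. First rescue: 1 − 12/21 = 42.86% against 1 − 21/22 × 12/20 = 42.73%. Ninth rescue: 1 − 14/22 × 12/13 = 41.26% against 1 − 13/22 = 40.91%. Differences 0.13 and 0.35 points.

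**The case against.** The strongest reply is that the two places can be read together. Table 8-5 prints no date, and 8.2.5 sits under a definitions label and supplies the only explicit one. The earliest-AE tie-break suggests onset was a deliberate choice. The specific TEAE clause would then take precedence over the general clause that follows it, and the protocol's reference to the event could mean the adverse event. That reading is available and would settle which date to use. It does not help the analysis, because it makes the onset rule operative and an observed rescue after onset is then always discarded.

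Other points carry some weight. The protocol's instruction that "the use of rescue therapy should be delayed, if possible, for at least 2 days following the administration of study treatment" runs from dosing, not from TEAE onset, so it says little about the gap between onset and rescue. The case does not need it.

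Steroid for anaphylaxis may fall on the onset day itself. The usual Kaplan-Meier convention places events before censorings at tied times, but it orders the records of different participants. It does not decide whether one participant's record is coded as an event or a censoring, and the SAP gives no rule for that.

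The objection is right about size. The number of affected participants is unknown. Protocol 2.2 reports no TEAEs leading to discontinuation of study drug in the completed Phase 2 ITP study, though with only 1 to 5 doses. The SAP names the median, not cumulative percentages, as the Kaplan-Meier output. Efficacy data are also listed by participant, so a lost rescue would remain visible there.

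**Conclusion.** The concern holds. SAP 8.2.5 and Table 8-5 point to different censoring dates. The one date that is written out, TEAE onset, is the wrong choice because it removes rescue observed between onset and withdrawal.

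The two rules give the same event status only when no first rescue falls in that interval. Even then, the onset rule shortens time at risk for TEAE withdrawals.

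The impact is small and may be nil: a descriptive secondary endpoint, 33 participants, no hypothesis test. The sizes shown rest on an assumed 22 and 11 split, assumed rescue counts and positions, and no other censoring before the last rescue. They show what one or a few such participants would do, not what the data will show. It should still be corrected, because the rule is wrong as written and easy to change.

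**What to change.** In SAP 8.2.5:

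- Count any first rescue on or before the date of withdrawal as an event, including rescue on the day of TEAE onset.
- Censor TEAE withdrawals without rescue at the date of withdrawal.
- Delete the TEAE-start wording and the earliest-AE sentence.

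In Table 8-5, row a, state the same date and name the recorded field. The date of discontinuation already used in SAP Table 4-1 would serve.

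The cost is wording in two places, one date derivation and one Kaplan-Meier table. No new data are needed, and the estimates may not change.

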8.2.5.1 Estimand’s attributes

The same considerations for treatment conditions and population of interest as mentioned in items 1 and 2 in Section 8.1.1, except the endpoint which is described above and the following approach for ICE (see Table 8-5) and the population level summary:

Table 8-5: Intercurrent Events (ICE), Intercurrent Events Strategies (ICES) and Missing data Strategies for the analysis of Time to first rescue therapy

Intercurrent Events (ICE)	ICE Strategy	Missing data strategy
a) Withdrawal from the study due to TEAE	A composite strategy: Participants will be considered censored at the time of the ICE.	Not applicable
b) COVID-19*	A composite strategy:	Section 4.2.2

* COVID-19 Impact category: Temporary discontinuation of study drug, Permanent discontinuation of study drug, Termination of study participation and Relationship to COVID-19: confirmed, suspected, general or other as recorded in the COVID-19 impact eCRF form.

Population level summary: Endpoint will be descriptively summarized. Median time to event will be estimated using the Kaplan-Meier estimate.

8.2.6 Change from Baseline to Week 25 in ITP-PAQ Symptom score

Change in ITP-Patient Assessment Questionnaire (ITP-PAQ, see section 8.1.3.1 in the protocol for details) Symptom score will be calculated at week 25 relative to the Baseline and will be

limited to the participants with a Baseline ITP-PAQ score available. Endpoint will be descriptively summarized. Please see Section 13.5 for details about ITP-PAQ scoring and ITP-PAQ scales.

8.3 Statistical analysis of other efficacy endpoints

8.3.1 Cumulative number of weeks over the planned 24-Week treatment period with platelet counts $\geq 30 \times 10^9/L$ and at least doubling from Baseline.

Cumulative number of weeks over the planned 24-Week treatment period with platelet counts $\geq 30 \times 10^9/L$ and at least doubling from Baseline will be summarized descriptively using the RS and listed.

The same considerations for treatment conditions and population of interest as mentioned in items 1 and 2 in Section 8.1.1, except the endpoint which is described above and the following approach for ICE (see Table 8-6) and the population level summary:

Table 8-6: Intercurrent Events (ICE), Intercurrent Events Strategies (ICES) and Missing data Strategies for the analysis of cumulative number of weeks over the planned 24-Week treatment period with platelet counts $\geq 30 \times 10^9/L$ and at least doubling from Baseline..

Intercurrent Events (ICE)	ICE Strategy	Missing data strategy
a) Use of rescue therapy prior to Week 25	Composite strategy: Participants impacted by any of these ICE of interest will be considered as non-responders.	Participants with missing values due to any of these ICE of interest will be considered as non-responders.
b) TEAEs leading to permanent treatment discontinuation		
c) Discontinue prior to receiving IMP		
d) Study participant do not have a valid Baseline assessment		
e) COVID-19*	Composite Strategy: Participants impacted by ICE (e) will be considered as non-responders at the time of event.	Section 4.2.2

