Platelet Count	Secondary/MCP	Cumulative number of weeks with Clinically Meaningful Platelet Response of $\geq 50 \times 10^9/L$ over the 24-week treatment period	RS who were randomized to rozanolixizumab weekly dosing compared against those who received placebo.	A composite endpoint will be used where, in the case rescue therapy are taken, only the platelet data up to the start date of rescue therapy will be utilized for the statistical analysis. Participants who take rescue therapy or who are withdrawn owing to TEAEs are defined as having a loss of durable platelet response at the time of the event occurring.	Cumulative number of weeks with clinically meaningful platelet response will be analyzed using an analysis of covariance with fixed terms for treatment, splenectomy, degree of thrombocytopenia (platelet count < or $\geq 15 \times 10^9/L$). Estimated means and 95% CI will be presented for each treatment group.
Platelet Count	Secondary/MCP	Time to first Clinically Meaningful Platelet Response of $\geq 50 \times 10^9/L$: time from starting treatment to achievement of first response of $\geq 50 \times 10^9/L$	RS who were randomized to rozanolixizumab weekly dosing compared against those who received placebo.	A composite strategy will be used where, in the case rescue therapy are taken, only the platelet data up to the start date of rescue therapy will be utilized for the statistical analysis. Participants who take rescue therapy or who are withdrawn due to TEAEs are defined as having a loss of clinically meaningful platelet response and will be censored at the time of the event.	Time to first Clinically Meaningful Response will be analyzed using a stratified Log Rank Test with fixed terms for treatment, splenectomy, degree of thrombocytopenia (platelet count < or $\geq 15 \times 10^9/L$). Estimated hazard ratios and 95% CIs will be presented. The time to first Clinically Meaningful Response will

Objective Clinical Category	Statistical Category	Estimand			
		Variable/Endpoint	Population	IES ^a	PLS ^b (Analysis)
					be presented graphically using a Kaplan-Meier curve.

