8.1 Statistical analysis of the primary efficacy endpoint

8.1.1 Primary analysis of the primary efficacy endpoint

The primary efficacy endpoint will be analyzed according to the following estimands' attributes:

- (1) Treatment conditions: Placebo and rozanolixizumab (please refer to section 6 Study treatments in the protocol for details)
- (2) Population: Adult Study Participants with Persistent or Chronic Primary Immune Thrombocytopenia (ITP) who fulfill the inclusion / exclusion criteria according to the protocol.
- (3) Endpoint: Durable Clinically Meaningful Platelet Response of $\geq 50 \times 10^9/L$, for at least 8 out of 12 weeks during the last 12 weeks (Week 13 to Week 25)
This endpoint includes the platelet count recorded at Week 14 to Week 25 corresponding to the response achieved following dosing at Week 13 to Week 24)
- (4) Intercurrent Events: see below.

Table 8-1: Intercurrent Events (ICE), Intercurrent Events Strategies (ICES) and Missing data Strategies for the analysis of the primary endpoint

Intercurrent Events (ICE)	ICE Strategy	Missing data strategy
a) Use of Rescue therapy from Baseline prior Week 25	A composite strategy Participants impacted by any ICE (a, b, c and d) will be considered as non-responders after the time of event.	Not applicable Section 4.2.2
b) Participants who experience any TEAEs leading to permanent treatment discontinuation		
c) Participants who discontinue prior to receiving IMP		
d) Participants who do not have any post-treatment assessment		
e) COVID-19*	A composite strategy Participants impacted by ICE (e) will be considered as non-responders at the time of event.	

* COVID-19 Impact category: Temporary discontinuation of study drug, Permanent discontinuation of study drug, Termination of study participation and Relationship to COVID-19: confirmed, suspected, general or other as recorded in the COVID-19 impact eCRF form.

(5) Population-level summary: Owing to early termination of the study, the population-level summary will be provided using descriptive statistics.

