8.2 Statistical analysis of the secondary efficacy endpoints

8.2.1 Cumulative number of weeks with Clinically Meaningful Platelet Response of $\geq 50 \times 10^9/L$ over the 24-Week treatment period (Week 1 to Week 25)

The secondary efficacy endpoint: Cumulative number of weeks with Clinically Meaningful Platelet Response of $\geq 50 \times 10^9/L$ over the 24-week treatment period will be analyzed on the RS, under the same treatment conditions and population of interest as for the primary endpoint. Note: if platelet count was assessed multiple times in a given week, Clinically Meaningful Platelet Response only needed to be observed at one timepoint during the week. ICE, ICES and population level summary will be handled as described below:

Table 8-2: Intercurrent Events (ICE), Intercurrent Events Strategies (ICES) and Missing data Strategies for the analysis of the Cumulative number of weeks with Clinically Meaningful Platelet Response of $\geq 50 \times 10^9/L$ over the 24-Week treatment period

Intercurrent Events (ICE)	ICE Strategy	Missing data strategy
a) Use of rescue therapy	A while on-treatment strategy: Participants impacted by	Participants impacted by any of the ICE will be considered as having a loss
b) Withdrawal from the study due to treatment emergent AE		

Intercurrent Events (ICE)	ICE Strategy	Missing data strategy
c) Permanent treatment discontinuation	any of the ICE will be considered as having a loss of durable platelet response at the time of the ICE occurring.	of durable platelet response at the time of the ICE occurring. Platelet data up to the start date of this ICE will be utilized in statistical analysis.
d) COVID-19*	A composite strategy: data impacted by COVID-19 will be considered as having a loss of durable platelet response at the time of the ICE occurring.	Section 4.2.2

* COVID-19 Impact category: Temporary discontinuation of study drug, Permanent discontinuation of study drug, Termination of study participation and Relationship to COVID-19: confirmed, suspected, general or other as recorded in the COVID-19 impact eCRF form.

Population-level summary: Owing to early termination of the study, the population-level summary will be provided using descriptive statistics.

8.2.2 Time to first Clinically Meaningful Platelet Response of $\geq 50 \times 10^9/L$: time from starting treatment to achievement of first response of $\geq 50 \times 10^9/L$.

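### SAP Table 8-6 applies a yes/no non-responder rule to a count of weeks, without a time limit or a value in weeks, and read literally it discards weeks already achieved

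*SAP*

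**What the plan says.** SAP 8.3.1 defines a count, reported by descriptive statistics and a listing: "Cumulative number of weeks over the planned 24-Week treatment period with platelet counts $\geq 30 \times 10^9/L$ and at least doubling from Baseline will be summarized".

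Table 8-6 names five intercurrent events. Rows a to d are rescue ("a) Use of rescue therapy prior to Week 25"), TEAEs leading to permanent discontinuation, discontinuation before IMP, and no valid Baseline. They share one rule: "Composite strategy: Participants impacted by any of these ICE of interest will be considered as non-responders". The missing-data column repeats it in nearly the same words. Row e, COVID-19, differs: "Participants impacted by ICE (e) will be considered as non-responders at the time of event".

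Two neighbouring tables handle the same kinds of event with a time limit:

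- Table 8-1 (primary endpoint, binary): "Participants impacted by any ICE (a, b, c and d) will be considered as non-responders after the time of event".
- Table 8-2 (weeks at 50 or above, also a count) uses a while-on-treatment strategy for events other than COVID-19: "Platelet data up to the start date of this ICE will be utilized in statistical analysis".

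For the count at 50, protocol Table 9-2 likewise says that after rescue "only the platelet data up to the start date of rescue therapy will be utilized for the statistical analysis". The protocol gives no estimand for the count at 30 with doubling.

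**The concern.** Non-responder is a category and the endpoint is a number, so the programmer has to decide what it means in weeks. The plain participant-level reading is zero for the whole 24-week period, including qualifying weeks before the event.

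Two things are at stake. First, two cumulative-week summaries in the same report would follow different rules with no reason given, and for many participants the less demanding criterion could show fewer weeks than the stricter one. Second, the trigger is broad. Protocol 6.4.3 counts as rescue any rise in concomitant ITP therapy above the Baseline dose, and systemic corticosteroids given for infusion reactions or other medical conditions. A late steroid course for an unrelated reason could therefore remove months of recorded response. This is one of only two endpoints in the other-efficacy group that SAP 3.9 keeps for summary.

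**Working it through.** The plan attaches no figure to this endpoint, so there is none to reproduce. The check scores constructed participants under the two rules.

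**Inputs**

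- Criterion A: count ≥ 50 (SAP 8.2.1). Criterion B: count ≥ 30 and ≥ 2 × Baseline (SAP 8.3.1).
- Baseline B₀ can reach 35, because inclusion criterion 8 (protocol 5.1) allows a single count up to that value.
- 33 randomized and a 2:1 ratio (SAP 2.3). The arm sizes are not stated; 22 and 11 are assumed.
- Assumed for illustration: one constant weekly count at Weeks 2 to 25 (24 weeks) and rescue at Week r.

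**Step 1: when does A imply B?** Criterion B needs a count of at least max(30, 2 × B₀). Every count ≥ 50 meets it if max(30, 2 × B₀) ≤ 50, that is, if B₀ ≤ 25. In that range, weeks under B cannot be fewer than weeks under A unless the event rule makes them so.

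**Step 2: score one participant.** B₀ = 10 and a count of 60 every week, so each week meets both criteria. Under Table 8-2 the score is the number of weeks from 2 to r − 1, which is r − 2. Under Table 8-6 read literally it is 0 after any rescue before Week 25.

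| Rescue at | Weeks ≥ 50 (Table 8-2) | Weeks ≥ 30 and doubled (Table 8-6, literal) | Same, counted up to the event |
|---|---|---|---|
| Week 5 | 3 | 0 | 3 |
| Week 14 | 12 | 0 | 12 |
| Week 20 | 18 | 0 | 18 |
| Week 24 | 22 | 0 | 22 |
| none | 24 | 24 | 24 |

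Without an event the counts agree. With one, the whole reversal comes from the rule, and it disappears when weeks are counted up to the event.

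**Step 3: outside the nested range.** With B₀ = 30, doubling needs a count of 60. Constant counts of 55 and no event give 24 weeks under A and 0 under B. Above a Baseline of 25 the order can therefore reverse by definition of the endpoints.

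**Step 4: effect on an arm mean.** One participant with 15 qualifying weeks on criterion B, scored as 0, lowers the mean by 15/22 = 0.68 weeks in an arm of 22, or by 15/11 = 1.36 weeks in an arm of 11. This is a single case; the shift scales with the qualifying weeks lost.

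**The case against.** The strongest reply is that Table 8-6 never says zero weeks. Elsewhere the plan ties non-response to a time or visit: Table 8-1 after the event, and SAP 4.2.1 and 4.2.2 at the specific visit. Nor does the label composite imply failure for the whole period in these documents. Protocol Table 9-2 uses it for the count at 50 while keeping data up to rescue, and SAP Table 8-5 uses it for censoring. If rows a to d mean non-response only from the event onward, the reversal does not arise.

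That stands in part: zero is the literal reading but not the only one. It does not clear the table, because row e carries a time limit that rows a to d omit, and a reader would take the omission as intended.

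It is also fair that treating rescue as failure for the whole period is a legitimate choice, and that the protocol sets no estimand here for the SAP to contradict. But the SAP neither states that choice in weeks nor explains why the sister count is handled differently.

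Finally, all efficacy variables are listed by participant group and visit (SAP 8), so the earlier weeks remain visible. That limits the harm to the summary.

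**Conclusion.** The point holds for rows a to d. A binary participant-level rule is set for a count, without a time limit or a value in weeks. Followed as written, it discards qualifying weeks before the event and conflicts with Table 8-2. For a Baseline of 25 or less, it can by itself put the lower-criterion count below the count at 50 (12 against 0 in the Week 14 example). The size depends on reading non-responder as zero weeks. The shift of 0.7 or 1.4 weeks in an arm mean also depends on the assumed 22/11 split and one chosen case.

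A reader might infer three stronger things that the documents do not support:

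- That every intercurrent event wipes out the count. The COVID-19 row is limited to the time of the event.
- That the criterion of 30 with doubling is always the easier one. It is not when Baseline exceeds 25.
- That the arm with more rescue loses most. What is lost is qualifying weeks before the event, so an arm rescued often after few such weeks loses little. The direction between arms cannot be predicted.

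Severity is minor. The study was terminated with 33 randomized, the endpoint is in the other-efficacy group, its summary is descriptive, and no test is attached (SAP 3.9 and 4.7).

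**What to change.** Reword Table 8-6, in both the strategy and the missing-data columns, so that the score is given in weeks:

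- Rows a and b (rescue; TEAE leading to permanent discontinuation): count qualifying weeks up to the start of the event and score later weeks as no response, as in Table 8-2. Rename the strategy to match.
- Rows c and d (no IMP; no valid Baseline): score zero weeks.
- Row e: no change.

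Participants who never qualify, or who have the event before any qualifying week, will also score zero in the ordinary way.

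The cost is a change of table wording. The SAP 8.2.1 logic can be reused, and no new data are needed. There is a small downside: rescue would no longer count as failure for the whole period, so the quantity estimated changes. If the sponsor wants whole-period failure, the table should state zero weeks explicitly, and the report should note that the two counts follow different rules.
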